14.5 Vital Signs

Vital signs (systolic blood pressure, diastolic blood pressure, heart rate, respiratory rate, and body temperature) and weight will be summarized using descriptive statistics at baseline and at each subsequent visit. Change from baseline values will also be presented for each post-baseline assessment.

For each vital sign, shift table from baseline to each post-baseline assessments describing shifts to abnormality (normal-abnormal not clinically significant [NCS]-abnormal clinically significant [CS] at baseline versus normal-abnormal NCS-abnormal CS at post-baseline visit in a 3-by-3 contingency table) will be provided as well. Only patients with a baseline result and a result at the specified post-baseline visit for the parameter will be considered in the shift tables.

A listing of all vital sign assessments, including height and weight, will be provided. In addition, a separate listing will be provided for each parameter where a patient had at least one clinically significant or not clinically significant abnormal result.

14.6 ECGs

Descriptive statistics will be presented for data related to ECGs (HR, RR, PR, QRS, QT

M-14867-32

Statistical Analysis Plan Status: Version (17 Jan 2023)

interval, QTcB interval and QTcF interval) at each scheduled visit, with change from baseline values presented for post-baseline assessments.

Shift tables from baseline to each post-baseline assessments describing shifts to abnormality (normal-abnormal NCS-abnormal CS at baseline versus normal-abnormal NCS-abnormal CS at post-baseline visit) will be provided for overall interpretation (based on Investigator interpretation). Only patients with a baseline result and a result at the specified post-baseline visit will be considered in the shift tables.

A listing of all ECG assessments will be provided. In addition, a separate listing will be provided for overall interpretation where a patient had at least one clinically significant or not clinically significant abnormal result.

14.7 Physical Examinations

All physical examinations will be listed.

15 ADDITIONAL ANALYSES

15.1 Subgroup Analyses

Descriptive statistics will be provided for exploratory endpoints by subgroups: age (<65 and ≥65), sex (male/female), number of AK lesions in the TF at baseline (≤8 and >8), treatment area (face/scalp), history of skin cancer (yes/no), and Fitzpatrick skin type (I/II and III/IV/V/IV). Figures for exploratory endpoints will only be provided for overall and by subgroup of treatment area (face/scalp).

Additionally, exposure, compliance and local tolerability assessments will be provided by subgroup of treatment area (face/scalp).

No other subgroup analysis is planned for this study.

15.2 Other Analyses

No other analyses are planned for this study.

16 CHANGES TO ANALYSES SPECIFIED IN THE PROTOCOL

The changes made to analyses specified in the protocol are presented in [Table 3](#).

Table 3 [Changes to Analyses Specified in the Protocol](#)

Description of the Change	Rationale

Protocol states that Unscheduled tests will not be associated with any trial visit. However assessments performed at each study visit will be remapped based on windowing conventions specified in Section 7.3.
	
To minimize missing data in table reporting.

Protocol states that the number and percentage of patients who experience one or more AESI will be tabulated by AESI. However the number and percentage of patients who experience one or more AESI will rather be tabulated by SOC and PT.
	
The only type of AESI considered in this study is skin cancer.

M-14867-32

Statistical Analysis Plan Status: Version (17 Jan 2023)

Protocol states the number and percentages of patients with events, and number and percentage of events will be presented for TEAEs.	Only the number and percentages of patients with events, and the number of events will be reported. Percentages of events will not be reported.
Protocol states subgroup analyses for exploratory endpoints only.	Exposure, compliance and local tolerability assessments will also be provided by subgroup of treatment area (face/scalp).

M-14867-32

Statistical Analysis Plan Status: Version (17 Jan 2023)

17 REFERENCES

Not applicable.

18 APPENDICES

18.1 Appendix 1

Output Conventions

Tables, listings, and figures (TLFs) will be generated using SAS® and will be displayed on letter size paper with landscape orientation. A margin of 2.1, 2.5, 2.5, 2.1 cm should be on the top, right, left, and bottom, respectively, and 8 pt Courier New Bold font.

The header section will comprise the drug name or code, the protocol number (Almirall code for the trial), the page number (Page X of Y), the TLF number, the TLF titles (left aligned), the population. The footer section will include the TLF footnotes, the name of the program, and the date of the execution of the program. Please refer to the Almirall Statistical TLFs Generation Process for details.

Mean, median and quantiles will be displayed to one more decimal place than the original value; minimum and maximum will keep the same number of decimal places as the original value; standard deviation, standard error and CI will be displayed to two more decimal places than the original value. If derived parameters are to be summarized, the number of decimals of the derived values is to be chosen on a case-by-case basis, but the rule above applies.

For categorical summary tables, percentages will be reported to one decimal place. Percentages between 0 and 0.1 (both exclusive) will be displayed as “<0.1”. The denominator for each percentage will be the number of patients within the population per group, unless otherwise specified.

Listings will be ordered by patient number, date, visit (where applicable) and timepoint (where applicable). Imputed dates and imputed missing data will not be presented in the listings.

Dates & Times Format

Date and time (if available) will be presented in the format DDMMYYYY/HH:MM.

Presentation of Treatment Groups

When applicable, study treatments will be represented as follows in the different outputs:

Study Treatment Full Names	Study Treatment Output Names
Tirbanibulin 1%	Tirbanibulin

18.2 Appendix 2

Algorithm for Imputation of Start/End Date of Adverse Events and Prior/Concomitant Medications

Event Start Date Imputation

- Imputation of event end date should be done before imputation of event start date.
- Completely missing: Impute to the first study treatment date.
- Missing day and month: Impute to January 1st, unless year is the same as year of first study treatment dose then impute to the first study treatment date.
- Missing day: Impute to the 1st of the month, unless month and year are the same as month and year of first study treatment dose then impute to the first study treatment date.
- If imputed event start date is after event end date (imputed or not), set the event start date to the imputed event end date.

Event Start Time Imputation

- Imputation of event end time should be done before imputation of event start date.
- If the event date (imputed or not) is not the same as the first dose date or time part of the first dose date is missing, impute to 00:00.
- If the event date (imputed or not) is the same as the first dose date, impute to time part of first dose date.
- If the event start date (imputed or not) is equal to event end date and imputed event start time is after event end time (imputed or not), set the event start time to the imputed event end time.

Event End Date Imputation

- Completely Missing (not flagged as "ongoing"): Impute to the last contact date.
- Missing day and month: Impute to December 31st, unless year is the same as last contact date then impute to the last contact date.
- Missing day: Impute to the last day of the month, unless year and month are the same as year and month of last contact date then impute to the last contact date.

Event End Time Imputation

- Impute to 23:59.

Certificate Of Completion

Envelope Id: 318AF1C6E01848C48C0C1ACEA6D58ADA

Status: Completed

Subject: Your electronic signature is required by Innovaderm Research- M14867-32_SAP_Final_v1.0_20230117

Source Envelope:

Document Pages: 36

Signatures: 4

Envelope Originator:

Certificate Pages: 5

Initials: 0

PPD

AutoNav: Enabled

EnvelopeD Stamping: Enabled

Time Zone: (UTC-05:00) Eastern Time (US & Canada)

[name]

[name]

[name]

PPD

IP Address: PPD

Record Tracking

Status: Original

Holder: PPD

Location: DocuSign

17-Jan-2023 | 11:55

PPD

Signer Events**Signature****Timestamp**

PPD

PPD

Sent: 17-Jan-2023 | 12:00

Security Level: Email, Account Authentication
(Required)

Signature Adoption: Pre-selected Style

Viewed: 17-Jan-2023 | 12:02

Signature ID:

Signed: 17-Jan-2023 | 12:03

PPD

Using IP Address: PPD

With Signing Authentication via DocuSign password

With Signing Reasons (on each tab):

I am the author of this document

Electronic Record and Signature Disclosure:

Accepted: 26-Jul-2022 | 10:21

Sent: 17-Jan-2023 | 12:03

ID: PPD

Viewed: 19-Jan-2023 | 07:56

Security Level: Email, Account Authentication

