## 8.7 Patient Replacement Criteria

Patients who withdraw from the trial at any time will not be replaced.

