7 DATA HANDLING

7.1 Missing Data

No imputation will be made for missing data. See [Appendix 2](#) for handling of completely or partially missing dates and time for prior and concomitant medications and adverse events.

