8 ANALYSIS POPULATIONS

There will be one analysis population in this trial:

Safety population: The safety population will include all patients who have received at least one dose of study treatment.

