14.1 Local Tolerability Assessment

Local tolerability is assessed based on the review of the following signs in the treatment field: erythema, flaking/scaling, crusting, swelling, vesiculation/pustulation, and erosion/ulceration and will be evaluated both individually and as a composite score (total of the 6 individual scores ranging from 0 to 18). These signs will be graded as: 0=absent, 1=mild (slightly, barely perceptible), 2=moderate (distinct presence), and 3=severe (marked, intense). If one or more individual score is missing, the composite score will be set as missing.

The maximum local tolerability signs composite score across visits will be derived as the maximum local tolerability assessment (LTA) composite score observed post-baseline for a patient. The maximum local tolerability of individual signs across visits will be derived as the maximum LTA of an individual sign observed postbaseline for a patient.

Descriptive statistics will be presented for local tolerability signs composite score by visit, and for maximum local tolerability signs composite score across post-baseline visits. Frequency and percentages by visit of patients presenting any individual and composite local tolerability signs and associated CI based on exact Clopper-Pearson method will be presented. The presence of any individual and composite local tolerability sign is defined by a score of >0. Frequency and percentages by visit for specific local tolerability individual signs results and maximum local tolerability of individual signs across post-baseline visits will also be provided.

The 95% CI will be presented for the median of the maximum local tolerability composite score.

Figures presenting the number of patients with each local tolerability individual sign (absent/mild/moderate/severe) by visit, and a figure presenting the mean local tolerability composite score by visit will be produced.

The time to maximum LTA score for each individual sign and the time to maximum LTA composite score will be calculated as the time (in days) from the first dose of study treatment to the time of the first occurrence of the maximum LTA score observed post-baseline for each individual sign and composite score, respectively. That is, for each individual sign, time to maximum LTA, in days, will be calculated as follows:

(Date of first post-baseline occurrence of maximum LTA score for an individual sign – Date of first dose)

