14.2 Scarring, Hypopigmentation and Hyperpigmentation

The number and percentage of patients with absence or presence of scarring, hypopigmentation, and hyperpigmentation in the TF and associated 95% CIs will be presented separately at scheduled visits.

Shift tables representing the change from baseline in scarring, hypopigmentation, and hyperpigmentation in the TF will be provided separately as well. Only patients with a baseline result and a result at the specified post-baseline visit for the parameter will be considered in the shift tables.

Scarring, hypopigmentation and hyperpigmentation evaluations will be presented in a listing.

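### By-visit percentages and exact CIs for local signs, scarring and pigmentation default to the full safety population, so patients with no assessment at a visit dilute them

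*SAP*

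**What the plan says.** The general rule is in SAP 18.1 (Appendix 1, Output Conventions): "The denominator for each percentage will be the number of patients within the population per group, unless otherwise specified". SAP 8 defines a single population: "The safety population will include all patients who have received at least one dose of study treatment". Attendance at a given visit is not part of that definition.

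Two analysis sections depend on the rule. SAP 14.1 plans "Frequency and percentages by visit of patients presenting any individual and composite local tolerability signs and associated CI based on exact Clopper-Pearson method". SAP 14.2 plans "The number and percentage of patients with absence or presence of scarring, hypopigmentation, and hyperpigmentation in the TF and associated 95% CIs", separately by visit. Neither states a denominator. SAP 14.4 is equally silent for the by-visit frequencies of qualitative urinalysis results.

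The SAP does override the default elsewhere. For shift tables, 14.2 says: "Only patients with a baseline result and a result at the specified post-baseline visit for the parameter will be considered in the shift tables". SAP 9.1 gives disposition percentages their own denominators. For continuous variables, SAP 6.1 reports the number of non-missing observations, so mean scores rest on assessed patients only.

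On missing data, SAP 7.1 says "No imputation will be made for missing data" but sets no denominator. Protocol 11.8.2 adopts an observed-cases approach, for the exploratory endpoints only. Protocol 8.7 adds: "Patients who withdraw from the trial at any time will not be replaced".

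**The concern.** Safety and tolerability are the primary objective, and the by-visit sign scores and the pigmentation and scarring proportions are listed safety endpoints (SAP 4.1, 4.2.1). A programmer following the SAP literally would divide every by-visit count by the number dosed. Whenever someone has no assessment in a window, the percentage with a sign is then lower than the percentage among those examined, and it can never be higher.

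Three consequences follow at the same visit. The present and absent rows (or grades 0 to 3) do not sum to 100%. The exact interval treats unexamined patients as observations. The mean composite score and the percentage with a sign describe different sets of patients.

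The composite rule adds a small further loss. Under SAP 14.1, one missing item sets the composite to missing, so a patient who attends with a visible sign can leave the composite numerator and stay in the denominator.

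The face/scalp tables in SAP 15.1 are more sensitive. With about one-third of 100 patients treated on the scalp, roughly 33, each unassessed scalp patient is 1/33 = 3% of the base.

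**Working it through.** **Inputs.** From SAP 5: N = 100, and planning rates of 90% (at least one local sign), 8% (vesiculation/pustulation) and 12% (erosion/ulceration). From SAP 6.1 and 6.2: two-sided 95% Clopper-Pearson intervals. The fraction unassessed at a visit, m, is not given in either document, so 0-20% is assumed. The planning rates are used only as illustrative values of p; the SAP does not state them as prevalences at any visit.

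**The plan's own figures.** SAP 5 gives full CI widths of about 11%, 10% and 13%. The Wald width, 2 x 1.96 x sqrt(p(1-p)/100), is 11.76, 10.63 and 12.74 points. The Clopper-Pearson widths are 12.72, 11.64 and 13.67. The third stated figure agrees with Wald on rounding and the first two only by truncation. The text says approximately, and nothing below depends on these figures.

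**Dilution.** Let x patients show the sign among n assessed, with n = N(1-m).

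- Assessed-patient rate: p = x/n.
- Rate under the default: x/N = p(1-m).
- Loss: p x m.

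| Rate among assessed | m = 0 | m = 5% | m = 10% | m = 20% |
|---|---|---|---|---|
| 90% | 90.0 | 85.5 | 81.0 | 72.0 |
| 12% | 12.0 | 11.4 | 10.8 | 9.6 |
| 8% | 8.0 | 7.6 | 7.2 | 6.4 |

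**With exact intervals (N = 100, numbers unassessed assumed).**

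| Unassessed | Assessed denominator | Default denominator |
|---|---|---|
| 5 | 86/95 = 90.5% (82.8-95.6) | 86/100 = 86.0% (77.6-92.1) |
| 10 | 81/90 = 90.0% (81.9-95.3) | 81/100 = 81.0% (71.9-88.2) |
| 10 | 11/90 = 12.2% (6.3-20.8) | 11/100 = 11.0% (5.6-18.8) |
| 10 | 7/90 = 7.8% (3.2-15.4) | 7/100 = 7.0% (2.9-13.9) |

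In the second row, 9 assessed patients have no sign. The default prints 9.0% absent beside 81.0% present, a total of 90.0%. If the interval were instead built on the 90 assessed patients while the percentage kept N = 100, the printed 81.0% would fall below its own lower limit of 81.9%.

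For the rarer signs the default interval is also narrower: 18.8 - 5.6 = 13.2 points against 20.8 - 6.3 = 14.5 in the third row.

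**Against the truth.** Let q be the unknown sign rate among unassessed patients. The true rate in everyone dosed is (1-m)p + mq.

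- Error of the default figure: -mq. It is zero if q = 0.
- Error of the assessed-patient figure: m(p-q). It is zero if q = p.
- When q > p, both are too low, the assessed-patient figure by m(q-p) and the default by mq.
- The default is the closer of the two only when mq < m(p-q), that is, when q < p/2.

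**The case against.** The strongest reply is that the effect is probably small, and much of that reply stands.

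- **Missingness is limited.** Protocol 10.3.2 does not allow Day 5 to be skipped. Protocol 8.4 encourages patients who stop treatment to stay in the trial. SAP 7.3 maps early-termination and unscheduled assessments into contiguous windows. Only a patient with no assessment in the whole window is affected.
- **Rates are low where dropout accumulates.** Protocol 5.1.5 reports that signs in earlier trials peaked around Day 8 and were mostly resolved by Day 29. At an assumed late prevalence of 5% with 10% unassessed, the loss is 0.5 points.
- **Other outputs are largely spared.** A maximum score needs only one post-baseline assessment, and AE incidence properly uses everyone dosed.
- **The effect can be traced.** Counts accompany percentages and all the data are listed. No by-visit rate is named as primary and no inference is performed.
- **Table shells may specify another denominator.** They are not among the documents. They could change what is printed, but as written the SAP states a rule and does not override it.

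Several stronger readings are tempting, and the documents do not support them.

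- **That missing patients are recorded as sign-free, contrary to SAP 7.1.** They fall in neither row, so nothing is imputed and 7.1 is not contradicted.
- **That a patient who withdraws on Day 6 is lost to the Day 8 table.** The Day 8 window is Days 6 to 11, so an early-termination assessment on Day 6 counts there.
- **That the error always favours the product.** The absent row is diluted too, which understates resolution, and if the unassessed are truly sign-free the default figure is the correct one.
- **That the printed rate is the true rate times the fraction assessed.** The identity holds for the rate among assessed patients, not for the true rate.

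**Conclusion.** The point holds as a defect of specification. For by-visit percentages and exact intervals of local signs, scarring and pigmentation, the SAP as written uses all dosed patients, whether or not they were examined. Relative to the assessed-patient rate, the present percentage falls by p x m points: zero with complete data, 4.5 points at p = 90% and m = 5%, and 0.4 (8% x 5%) to 1.2 (12% x 10%) points for the rarer signs. The latter is small against exact interval widths of about 12 to 14 points at N = 100.

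These sizes rest on assumed missing rates and on planning rates that are not visit prevalences. The 90% to 81% case shows the mechanism and is not a forecast. The documents support neither a claim that the primary safety results will be materially biased nor a claim that assessed-patient rates are unbiased. They do support the narrower statement that percentages, intervals and means in the same tables would rest on different patients, in a trial whose primary objective is tolerability.

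**What to change.** In SAP 14.1 and 14.2, and for the by-visit qualitative urinalysis frequencies in 14.4, state that by-visit percentages and any exact intervals use safety-population patients with a non-missing assessment of that parameter in that analysis visit. Print that n and the number missing in each column. Keep the full safety population as the denominator for AE incidence.

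The cost is one or two sentences and a change to the table shells, with no new data. Reported sign rates become slightly higher wherever anyone is unassessed. The change does not correct bias if patients with worse (or milder) reactions are the ones who go unassessed; the printed number missing lets a reader judge how much room there is for that.
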